8. ASSESSMENT OF SAFETY

8.1. Specification of safety parameters

8.1.1. Clinical parameters

8.1.1.1. Blood pressure and heart rate

Vital signs consist of body temperature measurement, systolic (SBP) and diastolic (DBP) blood pressures and heart rate.

The measurements for blood pressure and heart rate should be made after at least 10 minutes rest in the supine position and after 2 minutes in the standing position, before venepuncture when times of each coincide (except pre-dose). In case of Holter recording, vital sign will be measured after PK sampling.

8.1.1.2. Physical and neurological examination

A physical examination including weight and evaluation of main body systems/regions, including: skin and mucous, ears/nose/throat, pulmonary, cardiac, gastro-intestinal and neurological systems. A complete neurological examination will be performed at screening, D-1, D1 (around T6h), D4 and for the cohorts 160 mg, 260 mg, 380 mg and 500 mg at D6.

Weight will be only measured at screening, D4 and for the cohorts 160 mg, 260 mg, 380 mg and 500 mg at D6.

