1.3. Summary of the known and potential risk and benefits to human subjects

There is no known (identified) risks to human subjects.

The subjects enrolled in the present study being healthy are not expected to derive any benefit from participating in the present study.

Some changes may be anticipated in humans and thus will be monitored accordingly during the clinical trial as mentioned in section 7.3.1 of the Investigator's Brochure (IB): potential risk of decrease in

appetite, potential risks of alteration of renal and liver function tests, hematology parameters, and glucose levels, as well as potential risk of Central Nervous System alteration. All details on these risks and overall guidance are described in the IB Section 7 (Summary and Guidance for the Investigator).

DNDI-6148 was shown to have no genotoxicity potential. The fertility and reproductive toxicity data available in rats and generated after 64 days of dosing indicate a potential risk for decreasing male fertility. A potential effect on female reproductive performance cannot be excluded in regard to the increase in preimplantation loss and mean number of resorptions observed in the female rats following 21 days of administration. In the absence of animal data on developmental toxicity, risk of human teratogenicity/fetotoxicity cannot be excluded [6]. Of note, no women of childbearing potential are planned to be included in the present clinical trial and measures to prevent any exposure through seminal fluid are in place.

Decrease in fertility in clinical trial participants is not expected, considering the maximum dose considered and duration of treatment planned in the single dose administration study. Findings in male animals, both related to sperm abnormalities and histopathological changes were reported after 64 days of repeated dosing, while no histopathological change was noted in the 28 days repeated dosing study in the same species. The likeliness of impact of a single dose of DNDI-6148 on human male fertility is thus very low.

Before receiving a single dose of DNDI-6148, male participants to the present clinical study should be informed of this concern on the fertility in rat after a long exposure (64 days) while no concern were identified after 28 days, and at a higher exposure than expected in human.

Information on compound from the same chemical class

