3. STUDY DESIGN

3.1. Evaluation criteria

3.1.1. Primary endpoint

Assessment of safety and tolerability of DNDI-6148 by evaluation of following parameters:

- Adverse Events,
- Physical examination (including body weight),
- Clinical neurological examination,
- Vital signs,
- 12-lead ECG,
- Clinical laboratory (including serum chemistry, hematology, hormonology and urinalysis)
- Psychological and cognitive examination (Columbia-Suicide Severity Rating Scale (C-SSRS) and Bond & Lader questionnaires).

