8.2. Study Procedure

8.2.1. Screening procedures

Screening procedures occur within 4 weeks (D-28 to D-1) before starting study medication.

Subject enrolment – Screening visit

Subjects will be screened within subject's panel of Eurofins Optimed or recruited via advertisements if necessary (in this case, the advertisement has to be submitted to the Ethics Committee for approval before use).

Dedicated recruitment officers will propose subjects to participate in this study. They will be first informed verbally about the study. Then an appointment will be scheduled at the clinical centre (selection visit). Before any screening assessment is performed, complete and detailed information about the aim, the consequences and the constraints of the trial will be given by a physician, both verbally and by reviewing the information leaflet and consent form. If subject agrees to perform the study, he will sign the Informed Consent form and a copy of the information leaflet and consent form will be given to subjects.

At the screening visit, each subject will undergo a complete medical history and a physical examination including blood pressure and heart rate measurements. The subject will undergo the following tests and procedures:

- A medical examination including age, ethnic origin, alcohol, caffeine and nicotine consumptions, previous medication usage, surgical and medical history;
- A complete physical examination including height (cm), weight (kg) and BMI (kg/m²);
- A complete neurological examination
- An alcohol breath test;
- Blood pressure (SBP and DBP) and heart rate in both supine position (after at least 10 minutes rest) and standing position (after 2 minutes), using an automatic sphygmomanometer;
- Body temperature
- Safety ECG,
- C-SSRS evaluation Bond & Lader questionnaire,
- A biological screening test, including:
 - Serology test: HBsAg, anti-HCV antibody, anti-HIV 1 and 2 antibodies,
 - Urine drug screen: amphetamines, benzodiazepines, cannabis, cocaine and opiates,
 - Hematology,
 - o Hemostasis,
 - Hormonology,
 - o Biochemistry,
 - Urinalysis (qualitative).

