8.2.2. Description by type of visit

D-1

- Subject admission;
- Diagnostic test of SARS-CoV-2;
- Alcohol breath test;
- Urine drug screen;
- Physical examination
- Complete neurological examination;
- AE/Concomitant medication check;
- Laboratory safety (hematology, biochemistry, hemostasis, hormonology and urinalysis) will be performed in order to have the results before the Day 1 morning drug administration);
- Blood pressure, heart rate and body temperature;
- ECG
- C-SSRS evaluation Bond & Lader questionnaire.

D1

- Before administration
 - Physical examination;
 - ECG in triplicate before the T0 dosing time
 - Blood pressure, heart rate and body temperature at T0h;
 - AE/Concomitant medication check;
 - Blood sampling (Pre-dose);
 - Predose urine sample;
 - Start of Holter recording 70 minutes before dosing;
 - Randomization.
- oral administration in fasting condition.
 - AE/Concomitant medication check (any time)
 - Complete neurological examination around T6h;
 - Blood pressure, heart rate and body temperature at T1h, T1h30 (only for the cohorts 10 mg, 20 mg, 40 mg and 80 mg), T2h, T2h30, T3h, T4h, T5h (only for the cohorts 160 mg, 260 mg, 380 mg and 500 mg), T6h, T12;
 - ECG in single at T1h, T2h, T3h, T4h, T6h, T9h, T12h;
 - C-SSRS evaluation Bond & Lader questionnaire around T6h;
 - Holter 24h-hours recording;
 - Blood sampling (T30min, T1h, T1h30min (only for the cohorts 10 mg, 20 mg, 40 mg and 80 mg),
 T2h, T2h30min, T3h, T4h, T5h (only for the cohorts 160 mg, 260 mg, 380 mg and 500 mg), T6h,
 T9h, T12h);
 - Urine collection:]T0-T12h],]T12h-T24h].

D2

- Physical examination;
- Laboratory safety (hematology, biochemistry, hemostasis and urinalysis);
- Blood pressure, heart rate and body temperature
- End of 24h Holter recording (after blood sampling T24h);
- AE/Concomitant medication check (any time);
- Blood sampling (T24h);
- ECG in single;
- Urine collection]T24h-T48h].

D3

- Blood pressure and heart rate and body temperature;
- ECG in single;
- Blood sampling (T48h);
- AE/Concomitant medication check.
- Urine collection]T48h- T72h].

D4: (end of study visit for the cohorts 10 mg, 20 mg, 40 mg and 80 mg))

- Physical examination (including weight);
- Complete neurological examination,
- Laboratory safety (hematology, biochemistry, hemostasis, hormonology and urinalysis);
- Blood pressure, heart rate and body temperature;
- ECG in single;
- C-SSRS evaluation Bond & Lader questionnaire;
- Blood sampling (T72h);

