11.1.2.2. Physical examination, neurological examination, ECG, vital signs and questionnaires

Physical examination, neurological examinations, ECGs, vital signs and questionnaires (C-SSRS, Bond and Lader VAS) recorded during the study will be individually listed and quantitative parameters will be summarised by using descriptive statistics.

For vital signs and ECG parameters, values and abnormalities (not clinically significant and clinically significant) will be described by dose group and overall, at screening, study baseline (D-1 or D1 pre-dose), each evaluation under treatment phase and at the end of the study.

Change between the value at baseline and the value at each evaluation under treatment phase and at end of study visit will be described for each parameter by dose group and overall.

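### Body weight is part of the primary safety endpoint but has no pre-dose value nearer than screening (as early as D-28), so any weight change spans a pre-dose gap of variable length

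*Protocol*

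**What the plan says.** Section 3.1.1 lists among the primary safety parameters "Physical examination (including body weight"). Section 8.1.1.2 sets the schedule: "Weight will be only measured at screening, D4 and for the cohorts 160 mg, 260 mg, 380 mg and 500 mg at D6".

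The rest of the protocol follows that schedule. The body weight row of Table 1 is marked at screening, D4 and D6 only. In 8.2.2 the wording "Physical examination (including weight") appears at D4 and D6, while the physical examinations on D-1, D1 and D2 are listed without weight.

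Screening may be as early as D-28. Table 1 gives the window as D-28 to D-2. Section 8.2.1 says: "Screening procedures occur within 4 weeks (D-28 to D-1) before starting study medication".

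On analysis, section 11.1.2.2 calls for listings and descriptive statistics of quantitative physical-examination data. It then describes vital signs and ECG "at screening, study baseline (D-1 or D1 pre-dose), each evaluation under treatment phase" and at study end. A last sentence asks for change from baseline for each parameter, by dose group and overall. It does not name weight.

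**The concern.** In Table 1 every other repeated safety measure has a value on D-1, on D1 before dosing, or both: physical and neurological examination, haematology, haemostasis, hormonology, biochemistry, urinalysis, vital signs, ECG and the questionnaires. Body weight alone has none, although subjects are admitted on the morning of D-1 and are examined on D-1 and again before dosing on D1.

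Any weight change therefore mixes 3 days (D4) or 5 days (D6) after dosing with a period at home before admission. The length of that period differs between subjects. A statistical analysis plan cannot repair this, because a weight that was not taken before dosing cannot be recovered. At stake is the precision of one primary-endpoint parameter in cohorts of 6 active and 2 placebo subjects.

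**Working it through.** The protocol states no figure on this point, so there is none to reproduce. The check is interval arithmetic, followed by a sensitivity calculation on assumed variability.

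**Inputs from the protocol**
- Pre-dose weighing: screening on D-k, with k from 2 to 28 (Table 1).
- Post-dose weighings: D4 in all cohorts, D6 in the 160 to 500 mg cohorts (8.1.1.2).
- Dosing on D1. Table 1 places T72h on D4 and T120h on D6, so these visits fall 3 and 5 days after dosing. There is no Day 0, so D-k counts as k days before dosing.

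**Share of the weighing interval that precedes dosing**

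To D4 the share is k/(k+3); to D6 it is k/(k+5).

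| Screening day | To D4 | To D6 |
|---|---|---|
| D-28 | 28/31 = 90% | 28/33 = 85% |
| D-14 | 14/17 = 82% | 14/19 = 74% |
| D-7 | 7/10 = 70% | 7/12 = 58% |
| D-5 | 5/8 = 63% | 5/10 = 50% |
| D-3 | 3/6 = 50% | 3/8 = 38% |
| D-2 | 2/5 = 40% | 2/7 = 29% |

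The share exceeds one half for k above 3 to D4, which is 25 of the 27 days in Table 1's window. To D6 it exceeds one half for k above 5, which is 23 of 27 days.

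**After adding a weighing**
- On D-1: 1/(1+3) = 25% to D4 and 1/(1+5) = 17% to D6, whatever the screening date.
- On D1 before dosing: 0% for both.

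**How much noise this could be (assumed values)**

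The protocol gives no SD for weight. Suppose weight drifts as a random walk with SD s per square-root day, and each of the two weighings carries day-to-day SD e. The pre-dose share of the variance of the change to D4 is s²k / [s²(k+3) + 2e²]. Take s from 0.05 to 0.3 kg and e from 0.3 to 0.7 kg.
- D-28, s = 0.05, e = 0.7: 0.07 / (0.0775 + 0.98) = 7%.
- D-28, s = 0.3, e = 0.3: 2.52 / (2.79 + 0.18) = 85%.
- D-2, same two corners: 0.005 / 0.9925, about 1%, and 0.18 / 0.63 = 29%.

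At the first corner, the SD of change is 1.03 kg from a D-28 weight against 0.99 kg from a D-1 weight. At the second it is 1.72 kg against 0.73 kg. The gain from a later weighing could be negligible or large, and the documents do not show which.

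**The case against.** The schedule is applied consistently, and the word *only* in 8.1.1.2 shows that it was chosen. Weight is not named in any stopping rule in 3.5, and it enters the escalation review only through the physical examination. The analysis is descriptive. Treatment is randomised on D1, after the gap, so active and placebo subjects share it. Across 8 cohorts there are 16 placebo subjects. All of this stands, and it keeps the point minor.

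Several stronger readings are tempting, and the protocol does not support them.

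- *The measured change is mostly pre-dose drift.* Most of the elapsed time is pre-dose for most screening dates, but a share of time is not a share of kilograms. The 7% to 85% range at D-28 shows how far the answer depends on assumed values.
- *Weight breaks the plan's own baseline definition.* The phrase "study baseline (D-1 or D1 pre-dose") stands in a sentence written for vital signs and ECG, and 8.1.1.1 does not count weight among vital signs. A change from baseline in weight is implied by the reference to each parameter, not expressly planned.
- *Weight is the measure of the appetite risk.* Section 1.3 names a "potential risk of decrease in" appetite among the changes to monitor, but does not tie it to weight. Loss of appetite could also be recorded as an adverse event.
- *Lifestyle restrictions in the gap drive the drift.* Section 8.2.3 allows alcohol and xanthines until 24 hours before D-1 and asks for a stable lifestyle. Only the bans on nicotine and sport apply throughout the gap.

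**Conclusion.** The point holds in a limited form. A primary-endpoint parameter has no pre-dose value closer than a screening visit that may be 28 days old. Up to 90% of the interval to D4, and up to 85% of the interval to D6, then precedes dosing; at the latest screening day in Table 1 the shares are 40% and 29%. These figures rest only on the visit calendar.

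The effect on the comparison with placebo is extra noise, not systematic bias, because both arms share the gap. A dose group's own mean change still contains any pre-dose change, and 2 placebo subjects per cohort average out little of it. The size of the noise cannot be stated, because the protocol gives no weight variability. Priority: minor.

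**What to change.** Add body weight to the physical examination on D-1, or on D1 before dosing, in Table 1, the detailed flow chart, 8.1.1.2 and 8.2.2. Use the same scale and conditions as at D4 and D6. State that weight change is the D4 (D6) value minus that weight, and keep the screening weight for BMI eligibility. The D1 option removes the pre-dose interval altogether; the D-1 option leaves one day.

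The cost is one weighing and one eCRF field per subject, at an examination already done in the unit.

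Section 3.3.3.2 already cites interim results from the first three cohorts, so this can help only subjects still to be dosed. For those already dosed, report the change from screening together with the number of days between screening and dosing.

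In the same edit, reconcile the end of the screening window: D-2 in Table 1, D-1 in 8.2.1.

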8.1.1.3. Electrocardiogram (ECG)

Single 12-lead ECGs will be recorded after at least 10 minutes in supine position using a Cartouch Cardionics® Device (in case of abnormality, a retest is allowed at a minimum of one-minute interval between 2 subsequent ECG). Baseline assessment will be conducted in triplicate, at a minimum 1-minute interval between 2 subsequent ECG.

ECGs should always be recorded before the PK sampling (if any), except pre-dose and holter recording.

Each ECG consists of a minimum 10 second recording of the 12 leads simultaneously, leading to a 12-lead ECG (25 mm/s, 10mm/mV) print-out with morphology, HR, PR, QRS, QT, QTc automatic correction evaluation QTcB, QTcF, including date, time, year of birth and number of the subject, signature of the research physician, and at least 3 complexes for each lead. The Investigator medical opinion and automatic values will be recorded in the eCRF. This print-out will be retained at the site level.

Electronic recordings will be transferred to the ECG central reading facility at the end of each day. Safety cohort reports will be prepared at the end of each cohort, to be provided to the Safety Review Committee for dose-escalation decision. Central reading values will be transferred into the clinical database at the end of the study and will prevail on the automatic values for the final ECG analysis.

8.1.2. Biological parameters

8.1.2.1. Routine laboratory observations

The biological tests will be performed by the Groupe Oriade Noviale, [name] [name], [name], [name], France.

The full biological test comprises:

Hematology:

Hemoglobin, hematocrit, Red Blood Cells (RBC), White Blood Cells (WBC), differential count, platelet count, reticulocytes count, Mean Corpuscular Volume (MCV), Mean Corpuscular Hemoglobin (MCH), Mean Corpuscular Hemoglobin Concentration (MCHC);

- Hemostasis:

Haptoglobin, International normalized ratio (INR), Prothrombin time (PT), activated partial thromboplastin time (aPTT),

- Hormonology:

TSH, free T3,

- Biochemistry:

Creatinine, fasting blood glucose, total proteins, electrolytes (sodium, potassium, chloride), alanine serine transferase (ASAT), alanine leucine transferase (ALAT), Gamma Glutamyl Transferase (GGT), alkaline phosphatases (ALP), creatine phosphokinase (CPK), total bilirubin and urea, total cholesterol;

8.1.2.2. Urinalysis

The urinalysis tests will be performed by Eurofins-Optimed.

Semi-quantitative ("dipstick") analysis will be performed for the following parameters: pH, ketone bodies, proteins, glucose, occult blood, leukocytes, density. If "dipstick" shows a positive result for protein, glucose, blood and leukocytes, a quantitative result will be performed by the Groupe Oriade Noviale, [name] [name], [name], [name].

8.1.2.3. Drug of abuse screening tests

Drug of abuse screening tests will be performed, at Eurofins Optimed, on urine samples. Screened drugs are amphetamines, benzodiazepines, cannabis, cocaine, opiates.

8.1.2.4. Serologies

It will consist of the determination of: HBs antigen (hepatitis B antigen), anti HCV antibody, anti HIV1/HIV2 and antibodies.

8.1.2.5. Diagnostic test of SARS-CoV-2

In order to detect the COVID-19 infection, the diagnostic test of SARS-CoV-2 will be performed by the Groupe Oriade Noviale, [name] [name], [name], [name], using a validated RT-PCR method, on nasopharyngeal samples.

8.1.2.6. Cognitive evaluation

Bond and Lader Visual Analog Scale (VAS) questionnaire (see appendix IV).

The Bond and Lader VAS [36] is a measure of subjective feelings using 16 bipolar pairs of adjectives such as alert-drowsy or calm-excited on a 100 mm VAS. This is an auto-questionnaire.

8.1.2.7. Columbia-Suicide severity rating scale (C-SSRS)

C-SSRS evaluation (see appendix V).

A Columbia-Suicide severity rating scale (C-SSRS) evaluation will be done.

8.1.3. Other parameters

8.1.3.1. Alcohol breath test

An alcohol breath test will be performed at the centre, at screening and D-1. The test will be performed using the alcohol breath device ref 7410 plus Drager.

8.1.4. Abnormal safety parameters

Before the subject is allowed to enter the study a full clinical evaluation, ECG and full biological test will be obtained and the absence of clinically significant abnormalities confirmed by the Investigator.

In case of abnormality of any safety parameters (clinical, biological and ECG parameters) during the conduct of the study, an assessment on clinical significance of the abnormality will be made and a comment will be recorded in the eCRF; If an abnormality is judged clinically significant, an AE will be recorded.

8.2. Study Procedure

8.2.1. Screening procedures

Screening procedures occur within 4 weeks (D-28 to D-1) before starting study medication.

Subject enrolment – Screening visit

Subjects will be screened within subject's panel of Eurofins Optimed or recruited via advertisements if necessary (in this case, the advertisement has to be submitted to the Ethics Committee for approval before use).

Dedicated recruitment officers will propose subjects to participate in this study. They will be first informed verbally about the study. Then an appointment will be scheduled at the clinical centre (selection visit). Before any screening assessment is performed, complete and detailed information about the aim, the consequences and the constraints of the trial will be given by a physician, both verbally and by reviewing the information leaflet and consent form. If subject agrees to perform the study, he will sign the Informed Consent form and a copy of the information leaflet and consent form will be given to subjects.

At the screening visit, each subject will undergo a complete medical history and a physical examination including blood pressure and heart rate measurements. The subject will undergo the following tests and procedures:

- A medical examination including age, ethnic origin, alcohol, caffeine and nicotine consumptions, previous medication usage, surgical and medical history;
- A complete physical examination including height (cm), weight (kg) and BMI (kg/m²);
- A complete neurological examination
- An alcohol breath test;
- Blood pressure (SBP and DBP) and heart rate in both supine position (after at least 10 minutes rest) and standing position (after 2 minutes), using an automatic sphygmomanometer;
- Body temperature
- Safety ECG,
- C-SSRS evaluation Bond & Lader questionnaire,
- A biological screening test, including:
 - Serology test: HBsAg, anti-HCV antibody, anti-HIV 1 and 2 antibodies,
 - Urine drug screen: amphetamines, benzodiazepines, cannabis, cocaine and opiates,
 - Hematology,
 - o Hemostasis,
 - Hormonology,
 - o Biochemistry,
 - Urinalysis (qualitative).

8.2.2. Description by type of visit

D-1

- Subject admission;
- Diagnostic test of SARS-CoV-2;
- Alcohol breath test;
- Urine drug screen;
- Physical examination
- Complete neurological examination;
- AE/Concomitant medication check;
- Laboratory safety (hematology, biochemistry, hemostasis, hormonology and urinalysis) will be performed in order to have the results before the Day 1 morning drug administration);
- Blood pressure, heart rate and body temperature;
- ECG
- C-SSRS evaluation Bond & Lader questionnaire.

D1

- Before administration
 - Physical examination;
 - ECG in triplicate before the T0 dosing time
 - Blood pressure, heart rate and body temperature at T0h;
 - AE/Concomitant medication check;
 - Blood sampling (Pre-dose);
 - Predose urine sample;
 - Start of Holter recording 70 minutes before dosing;
 - Randomization.
- oral administration in fasting condition.
 - AE/Concomitant medication check (any time)
 - Complete neurological examination around T6h;
 - Blood pressure, heart rate and body temperature at T1h, T1h30 (only for the cohorts 10 mg, 20 mg, 40 mg and 80 mg), T2h, T2h30, T3h, T4h, T5h (only for the cohorts 160 mg, 260 mg, 380 mg and 500 mg), T6h, T12;
 - ECG in single at T1h, T2h, T3h, T4h, T6h, T9h, T12h;
 - C-SSRS evaluation Bond & Lader questionnaire around T6h;
 - Holter 24h-hours recording;
 - Blood sampling (T30min, T1h, T1h30min (only for the cohorts 10 mg, 20 mg, 40 mg and 80 mg),
 T2h, T2h30min, T3h, T4h, T5h (only for the cohorts 160 mg, 260 mg, 380 mg and 500 mg), T6h,
 T9h, T12h);
 - Urine collection:]T0-T12h],]T12h-T24h].

D2

- Physical examination;
- Laboratory safety (hematology, biochemistry, hemostasis and urinalysis);
- Blood pressure, heart rate and body temperature
- End of 24h Holter recording (after blood sampling T24h);
- AE/Concomitant medication check (any time);
- Blood sampling (T24h);
- ECG in single;
- Urine collection]T24h-T48h].

D3

- Blood pressure and heart rate and body temperature;
- ECG in single;
- Blood sampling (T48h);
- AE/Concomitant medication check.
- Urine collection]T48h- T72h].

D4: (end of study visit for the cohorts 10 mg, 20 mg, 40 mg and 80 mg))

- Physical examination (including weight);
- Complete neurological examination,
- Laboratory safety (hematology, biochemistry, hemostasis, hormonology and urinalysis);
- Blood pressure, heart rate and body temperature;
- ECG in single;
- C-SSRS evaluation Bond & Lader questionnaire;
- Blood sampling (T72h);
- AE/Concomitant medication check;
- Discharge.

D5, only for the cohorts 160 mg, 260 mg, 380 mg and 500 mg

- Blood pressure and heart rate and body temperature;
- ECG in single;
- Blood sampling (T96h);
- AE/Concomitant medication check.

D6: end of study visit only for the cohorts 160 mg, 260 mg, 380 mg and 500 mg

- Physical examination (including weight);
- Complete neurological examination,
- Laboratory safety (hematology, biochemistry, hemostasis, hormonology and urinalysis);
- Blood pressure, heart rate and body temperature;
- ECG in single;
- C-SSRS evaluation Bond & Lader questionnaire;
- Blood sampling (T120h);
- AE/Concomitant medication check.

